9.4.2 ANALYSIS OF THE PRIMARY ENDPOINT(S)

The primary endpoints of MVPA, dietary risk, and veggie meter will be assessed using the linear model described in 9.4.1. A test of the appropriate interaction parameter at a significance level of 0.05 will serve as the test of the intervention's effect on each primary outcome.

9.4.3 ANALYSIS OF THE SECONDARY ENDPOINT(S)

The secondary endpoints (BMI, % Body Fat, WHR, BP, and cytokines), dietary risk, and veggie meter will be assessed using the linear model described in 9.4.1. A test of the appropriate interaction parameter at a significance level of 0.05 will serve as the test the intervention's effect on each primary outcome.

The tertiary endpoints (mindfulness, stress management, positive reappraisal, self-regulation, and self-efficacy dietary risk, and veggie meter will be assessed using the linear model described in 9.4.1. A test of the appropriate interaction parameter at a significance level of 0.05 will serve as the test the intervention's effect on each primary outcome

9.4.4 BASELINE DESCRIPTIVE STATISTICS

Descriptive statistics will be presented for study demographics and endpoints, by intervention group, in the following manner:

For continuous variables, means with standard deviations and range for variables with approximately normal distributions; median with IQR and range for variables that are not close to normally distributed.

For categorical variables, sample size and percents will be presented for each category.

Baseline comparison of participants randomized to HARMONY vs. NEEW will be conducted using t-tests (for approximately normal variables), Wilcoxon rank sum (for variables that are not approximately normal), and chi-square tests (for categorical or dichotomous variables; categories will be collapsed and/or Fisher's Exact test will be used if the cell counts do not support the chi-square test). These tests will each use an alpha level of 0.05.

For each primary and secondary endpoint, we will use linear mixed models to assess whether HARMONY, compared to NEEW, will yield greater improvement on each outcome measure from baseline to post-baseline timepoints.

9.4.5 PLANNED INTERIM ANALYSES

N/A

9.4.6 SUB-GROUP ANALYSES

N/A

9.4.7 TABULATION OF INDIVIDUAL PARTICIPANT DATA

For data sharing purposes, individual participant data will be listed by measure and timepoint.

9.4.8 EXPLORATORY ANALYSES

Other timepoints: The intervention effect will be examined on the 16- and 32-week primary and secondary outcomes. Using the models described in 9.4.1, the intervention effect will be estimated at 16-

and 32-weeks using the appropriate interaction parameters. These tests will be conducted at an alpha level of 0.025; this alpha level was selected using a Bonferroni correction because each outcome has two tests.

Mediation: mediation of the intervention effect on the primary outcomes will be tested by each of the tertiary outcomes over 48 weeks. To account for temporal precedence, these analyses will use values for mediators measured at 32 weeks and primary outcome measured at the end of 48 weeks. Mediation will first be assessed using each of the three potential mediators one at a time and then in combination, to assess the possibility of multiple mediation.

The indirect effect of the intervention will be estimated via the mediator(s), along with a 95% bias-corrected bootstrapped confidence interval. This effect will be interpreted to the extent that it is in a direction consistent with the mediation hypothesis. It is important to estimate and test for mediation even if there is no evidence of an overall intervention effect. It is possible that the test of mediated effect has more statistical power, and mediation can be found in the absence of an overall effect.

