9 STATISTICAL CONSIDERATIONS

9.1 STATISTICAL HYPOTHESES

Primary Endpoints:

For each primary outcome (MVPA, dietary risk, and veggie meter), at each of 16, 32, and 48 weeks, the statistical hypotheses are:

H0: The change in the outcome does not differ between intervention and control groups.

HA: The change in the outcome does differ between intervention and control groups.

Specifically, it is expected that AAW participating in an 8-session culturally relevant mindfulness intervention plus an exercise and nutrition education CM risk-reduction intervention will have greater sustained improvement in exercise and healthy eating behaviors at 16, 32, and 48 weeks post first intervention session, compared to AAW in an attention-control exercise and nutrition education CM risk-reduction intervention without mindfulness.

Secondary Endpoints:

For each secondary outcome (CM risk biomarker), at each of 16, 32, and 48 weeks, the statistical hypotheses are:

H0: The change in the outcome does not differ between intervention and control groups.

HA: The change in the outcome does differ between intervention and control groups.

It is hypothesized that AAW participating in an 8-session culturally relevant mindfulness intervention plus an exercise and nutrition education CM risk-reduction intervention will have greater reduction in CM risk biomarkers at 16, 32, and 48 weeks post first intervention session, compared to AAW in an attention-control exercise and nutrition education CM risk-reduction intervention without mindfulness.

Tertiary Endpoints:

Tertiary outcomes are self-reported mindfulness, stress management, positive reappraisal, self-regulation, and self-efficacy mediate effects of the intervention on exercise and nutrition.

For each tertiary outcome, at each of 16, 32, and 48 weeks, the statistical hypotheses are:

H0: The change in the outcome does not differ between intervention and control groups.

HA: The change in the outcome does differ between intervention and control groups.

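### Section 9.4.8 gives the mediation analysis no baseline mediator or baseline outcome term, so it can show false mediation or hide true mediation, and its direction sentence lets contrary effects go uninterpreted

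*Combined protocol and SAP*

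**What the plan says.** The mediation paragraph of section 9.4.8 fixes the timing: "these analyses will use values for mediators measured at 32 weeks and primary outcome measured at the end of 48 weeks". Its stated reason is "To account for temporal precedence". The indirect effect is to be estimated "along with a 95% bias-corrected bootstrapped confidence interval". On direction it says: "This effect will be interpreted to the extent that it is in a direction consistent with the mediation hypothesis". It adds: "It is important to estimate and test for mediation even if there is no evidence of an overall intervention effect".

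No regression equation is written, and no covariate is named as included or excluded. The paragraph just above it, on the 16- and 32-week effects, refers back to the section 9.4.1 models, which carry the endpoint's baseline value as a fixed effect. The mediation paragraph makes no such reference. It speaks of values at 32 weeks, whereas section 3 defines the same scales as changes from baseline, so raw score versus change is also open.

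**The concern.** Randomisation protects the path from intervention to mediator. It does not protect the path from mediator to outcome. Measuring the mediator 16 weeks before the outcome settles their order, but does not remove lasting differences between women. A woman with less stress or more self-efficacy at entry may also be more active at entry, and both traits persist. Section 2.2 reports associations of this kind in earlier samples: Superwoman Schema with physical inactivity and with eating to cope, and culturally relevant stress with stress-related eating and obesity. It gives no magnitudes.

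The analysis is exploratory, but it carries the trial's account of mechanism. Section 4.1 puts the main hypothesis in terms of better management of stress, section 9.2 gives mediation its own power statement, and mediation is to be tested even without an overall effect. In a trial with null primary results it could become the leading positive claim.

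**Working it through.** **Inputs from the documents.** n = 160 (80 per arm), both standardised paths at least 0.26, and stated power of at least 80% (section 9.2). The test is a 95% bias-corrected bootstrap interval (section 9.4.8).

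**Inputs assumed.** Stability r of mediator and outcome from baseline to follow-up, and baseline mediator-outcome correlation ρ. Section 9.2 gives correlations only for BMI (0.35), waist-hip ratio (0.11) and A1C (-0.45), and none for a mediator or a primary outcome.

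**Step 1: the plan's own figure.** The chance that both paths are significant is about [Φ(0.26 × √160 − 1.96)]² = [Φ(1.329)]² = 0.908² = 0.825. Simulating the planned bootstrap test gives 0.858. The stated power of at least 80% reproduces.

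**Step 2: how the bias arises.** Code every scale so that higher is better, and the arm as x = ±1. Let M₀ and Y₀ be standard normal with correlation ρ, and

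- M = 0.26x + rM₀ + √(1−r²)e₁
- Y = bM + rY₀ + √(1−r²)e₂

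with independent e₁ and e₂. If b = 0, M and Y still correlate within arm by r × r × ρ. The unadjusted analysis reads this as the mediator's effect. The approximate false rate is Φ(0.26√160 − 1.96) × Φ(r²ρ√160 − 1.96).

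- r = 0.6, ρ = 0.3: r²ρ = 0.108; 0.908 × Φ(1.366 − 1.96) = 0.908 × 0.276 = 0.25.
- r = 0.6, ρ = 0.5: r²ρ = 0.18; 0.908 × Φ(2.277 − 1.96) = 0.908 × 0.624 = 0.57.

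The bias-corrected bootstrap rejects somewhat more often than this approximation.

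**Step 3: simulation of the planned test, b = 0.** 1,500 trials per row, 1,000 resamples, Monte Carlo standard error at most 1.3 points. The entries are rates of an interval excluding zero in the hypothesised direction.

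| r | ρ | No baselines | Both baselines |
|---|---|---|---|
| 0.35 | 0.2 | 7.6% | 3.3% |
| 0.35 | 0.3 | 9.8% | 3.8% |
| 0.35 | 0.5 | 16.1% | 4.4% |
| 0.6 | 0.2 | 20.4% | 3.6% |
| 0.6 | 0.3 | 33.3% | 5.1% |
| 0.6 | 0.5 | 67.0% | 4.6% |

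A separate run of 1,000 trials gave 10.1% and 5.2% at (0.35, 0.3), and 32.6% and 3.7% at (0.6, 0.3). Outside this range, at r = 0.7 and ρ = 0.5, it gave 84.8% and 3.5%. With no baseline correlation the rate was 3.4% either way.

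**Step 4: opposite-sign correlation.** With a true b = 0.26, r = 0.6 and ρ = −0.3, the induced −0.108 offsets the true effect: 0.26 − 0.108 = 0.152. Simulated detection is 53% without baselines and 90% with both.

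**Step 5: where the problem is absent.** If the intervention does not move the mediator, the unadjusted rate in the hypothesised direction is 0.5% to 3.5%.

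**Step 6: the direction sentence.** With the mediator not moved, r = 0.7 and ρ = 0.5, 7.4% of unadjusted intervals exclude zero in either direction and 3.5% do so in the hypothesised one. Reading only the hypothesised sign lowers false claims.

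**Step 7: confounding after baseline.** With ρ = 0, r = 0.6 and a correlation of 0.2 between e₁ and e₂, the false rate is 40.9% unadjusted and 74.5% adjusted. Adjustment removes the stable variance that diluted the residual link: (1 − 0.36) × 0.2 = 0.128 before, 0.2 after.

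**The case against.** The strongest reply is that section 9.4.8 is silent on baseline and does not rule it out. The plan uses baseline values elsewhere, in the 9.4.1 models and the section 3 definitions. If the mediation outcome model inherited the baseline outcome term from 9.4.1, the inflation would be gone in these scenarios. That stands as a possibility. But the mediation paragraph does not invoke 9.4.1, and an analyst following it literally would leave the term out. Nor would change scores alone settle the matter: without a baseline covariate they still gave false mediation in 13% to 33% of trials at stability 0.6.

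Three stronger readings are tempting, and the documents support none of them.

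- A reader might infer that the analysis will find mediation where none exists. It needs both a moved mediator and a same-sign baseline correlation, and the documents do not quantify the second.
- A reader might infer that the direction sentence inflates false positives, or restricts interpretation to one sign. The interval stays two-sided, estimation and reporting are not suppressed, and the wording is a matter of extent. Step 6 shows that one-sided reading lowers false claims.
- A reader might infer that baseline adjustment makes the mediation estimate causal. Step 7 shows that it does not.

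The exploratory label also stands: no primary or secondary test is affected. Testing mediation without a total effect is stated in advance with a reason and is not a fault.

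**Conclusion.** The concern holds as a gap in specification with a real consequence. Followed as written, section 9.4.8 can give false mediation at about 10% to 65% over the assumed range (7.6% to 67.0% in the table), against about 3% to 5% with both baselines, and it can hide true mediation when the baseline correlation has the opposite sign. These figures rest on n = 160, a mediator moved by a standardised 0.26 (the smallest path at which section 9.2 claims at least 80% power), equal stability for mediator and outcome, and no confounding after baseline. The direction sentence is a separate and smaller fault: it permits a contrary indirect effect, such as a mediator that goes with worse diet or activity, to pass without comment. The change should be made because it is free and the mechanism claim depends on it. It does not bear on the primary conclusions.

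**What to change.** In section 9.4.8:

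1. Write both equations, with the baseline mediator M₀ and baseline outcome Y₀ in each:
   - M₃₂ = i₁ + a·arm + d₁M₀ + d₂Y₀ + e₁
   - Y₄₈ = i₂ + c·arm + b·M₃₂ + d₃M₀ + d₄Y₀ + e₂

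   The indirect effect is a × b. State that M₃₂ and Y₄₈ are scores at the visit, not changes. The multiple-mediator model takes the baseline of each mediator in it.
2. Replace the direction sentence with a statement that every indirect effect and its 95% interval is reported and interpreted whatever its sign.
3. State that baseline adjustment does not remove mediator-outcome confounding arising after baseline. Add a sensitivity analysis that varies the correlation between e₁ and e₂ over a stated range and reports where the interval first includes zero.
4. While rewriting, name the mediators: section 9.4.8 counts three ("Mediation will first be assessed using each of the three potential mediators one at a time and then in combination"), while section 9.1 lists five constructs.

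The cost is SAP wording and a little programming. The schedule in section 1.2 already collects the mediator scales at screening, pre-baseline or baseline, and the three primary outcomes at baseline. No new data, visits or participants are needed.

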10 SUPPORTING DOCUMENTATION AND OPERATIONAL CONSIDERATIONS

10.1 REGULATORY, ETHICAL, AND STUDY OVERSIGHT CONSIDERATIONS

10.1.1 INFORMED CONSENT PROCESS

10.1.1.1 CONSENT/ASSENT AND OTHER INFORMATIONAL DOCUMENTS PROVIDED TO PARTICIPANTS

Verbal consent will be obtained from the participant prior to any study procedures.

Written consent will be obtained from the participant at their baseline visit. Consent forms describing in detail the study intervention, study procedures, and risks will be given to the participant at that visit and written documentation of informed consent will be completed prior to starting further study procedures.

10.1.1.2 CONSENT PROCEDURES AND DOCUMENTATION

Verbal consent from the participant will be obtained via telephone during the telephone screening visit. The telephone consent form describes the study intervention, procedures, and risks. Documentation of

verbal consent will be kept by the study team in the participant's file. Verbal consent will be obtained from the participant prior to sending their pre-baseline period questionnaires.

Written consent will then be obtained from the participant at the beginning of their baseline visit, prior to conducting any further study procedures.

For both verbal and written consent, the consent discussion will be led by study personnel delegated to conduct the consent process. Study personnel will explain the consent form to the subject, and the study subject will have the opportunity to ask any questions they may have regarding the consent before signing. The consent process will be documented in the participant's study file.

For written consent, a copy of the consent will be given to the patient for their records.

10.1.2 STUDY DISCONTINUATION AND CLOSURE

This study may be temporarily suspended or prematurely terminated if there is sufficient reasonable cause. If the study is prematurely terminated or suspended, the Principal Investigator (PI) will promptly inform study participants, the Institutional Review Board (IRB), and the NIH and will provide the reason(s) for the termination or suspension. Study participants will be contacted, as applicable, and be informed of changes to study visit schedule.

Circumstances that may warrant termination or suspension include, but are not limited to:

- Determination of unexpected, significant, or unacceptable risk to participants
- Demonstration of efficacy that would warrant stopping
- Insufficient compliance to protocol requirements
- Data that are not sufficiently complete and/or evaluable
- Determination that the primary endpoint has been met
- Determination of futility

The study may resume once concerns about safety, protocol compliance, and data quality are addressed, and satisfy the funding agency, IRB, or other relevant regulatory or oversight bodies.

10.1.3 CONFIDENTIALITY AND PRIVACY

Participant confidentiality and privacy is strictly held in trust by the study staff, the safety and oversight monitor(s), and the funding agency. This confidentiality is extended to the data being collected as part of this study. Data that could be used to identify a specific study participant will be held in strict confidence within the research team. No personally identifiable information from the study will be released to any unauthorized third party without prior written approval of the sponsor/funding agency.

All research activities will be conducted in as private a setting as possible. However, due to the nature of the online group intervention, participants may talk about personal experiences in a group setting. Participants will be instructed to not reveal private information about other group members to others. In addition, participants will be asked to attend group sessions in a private area.

The study monitor, other authorized representatives of the sponsor or funding agency, representatives of the Institutional Review Board (IRB), or regulatory agencies may inspect all documents and records required to be maintained by the investigator, including but not limited to, study records for the participants in this study. The study site will permit access to such records.

The study participant's contact information will be securely stored at each clinical site for internal use during the study. At the end of the study, all records will continue to be kept in a secure location for as long a period as dictated by the reviewing IRB, Institutional policies, or sponsor/funding agency requirements.

Study participant research data, which is for purposes of statistical analysis and scientific reporting, will be and stored at UNC Chapel Hill. Individual participants and their research data will be identified by a unique study identification number. The study data entry and study management systems used by clinical sites and by research staff will be secured and password protected. At the end of the study, all study databases will be de-identified and archived at UNC Chapel Hill.

Measures Taken to Ensure Confidentiality of Data Shared per the NIH Data Sharing Policies

It is NIH policy that the results and accomplishments of the activities that it funds should be made available to the public (see <https://grants.nih.gov/policy/sharing.htm>). The PI will ensure all mechanisms used to share data will include proper plans and safeguards for the protection of privacy, confidentiality, and security for data dissemination and reuse (e.g., all data will be thoroughly de-identified and will not be traceable to a specific study participant). Plans for archiving and long-term preservation of the data will be implemented, as appropriate.

Certificate of Confidentiality

To further protect the privacy of study participants, the Secretary, Health and Human Services (HHS), has issued a Certificate of Confidentiality (CoC) to all researchers engaged in biomedical, behavioral, clinical or other human subjects research funded wholly or in part by the federal government. Recipients of NIH funding for human subjects research are required to protect identifiable research information from forced disclosure per the terms of the NIH Policy (see <https://humansubjects.nih.gov/coc/index>). As set forth in 45 CFR Part 75.303(a) and NIHGPS Chapter 8.3, recipients conducting NIH-supported research covered by this Policy are required to establish and maintain effective internal controls (e.g., policies and procedures) that provide reasonable assurance that the award is managed in compliance with Federal statutes, regulations, and the terms and conditions of award. It is the NIH policy that investigators and others who have access to research records will not disclose identifying information except when the participant consents or in certain instances when federal, state, or local law or regulation requires disclosure. NIH expects investigators to inform research participants of the protections and the limits to protections provided by a Certificate issued by this Policy.

10.1.4 FUTURE USE OF STORED SPECIMENS AND DATA

Data collected for this study will be analyzed and stored at UNC Chapel Hill. After the study is completed, the de-identified, archived data will be stored for use by other researchers including those outside of the study to comply with NIH guidelines for sharing of study data. This data sharing will ensure that confidential information is not disclosed, data are released in a form that does not endanger national security or compromise law enforcement activities, and that proprietary data are not released inadvertently.

With the participant's approval and as approved by local Institutional Review Boards (IRBs), de-identified biological samples will be stored at UNC Chapel Hill. These samples could be used to research the increased risk of cardiometabolic conditions in African American and Black women and to improve treatment.

During the conduct of the study, an individual participant can choose to withdraw consent to have biological specimens stored for future research. However, withdrawal of consent with regard to biosample storage may not be possible after the study is completed.

When the study is completed, access to study data and/or samples will be provided through UNC Chapel Hill.

10.1.6 SAFETY OVERSIGHT

Oversight for this study will be provided by the MPIs with delegation of responsibilities to designated study personnel. The Safety Officer will review the all reports of adverse events quarterly and when

necessary, make recommendations to the MPIs concerning continuation, termination or modification of any study protocol/ procedure based on observed beneficial or adverse effects.

10.1.7 DATA HANDLING AND RECORD KEEPING

10.1.7.1 DATA COLLECTION AND MANAGEMENT RESPONSIBILITIES

Data collection will be the responsibility of the study staff under the supervision of the MPIs. The investigator will be responsible for ensuring the accuracy, completeness, legibility, and timeliness of the data reported.

All source documents will be completed in a neat, legible manner to ensure accurate interpretation of data.

Any hardcopies of the study visit worksheets will be provided for use as source document worksheets for recording data for each participant consented/enrolled in the study. Data recorded in the electronic case report form (eCRF) derived from source documents will be consistent with the data recorded on the source documents. In many cases, the data will be entered directly into the eCRF, in those cases, the eCRF will be considered source.

Data (including adverse events (AEs), concomitant medications, and expected adverse reactions data) will be entered into REDCap. The data system includes password protection and quality features to identify data that appear inconsistent, incomplete, or inaccurate. Clinical data will be entered directly from the source documents.

